Dexcel Pharma Technologies Ltd.

**The Efficacy and Safety of Chlorhexidine Gluconate
Chip (PerioChip[®]) in Therapy of Peri-implantitis**

Summary of Protocol Changes

Protocol Number: CLI/016P

NCT Number NCT02080403

EudraCT Number: 2013-000383-28

Sponsor: Dexcel Pharma Technologies Ltd.

Date: 13/April/2021

TABLE OF CONTENTS

[Summary of changes from version 1 dated 02 Nov. 2013 to version 2 dated 22 Jan. 2014](#)

[Summary of changes from version 2 dated 22 Jan. 2014 to version 3 dated 13 July 2014](#)

[Summary of changes from version 3 dated 13 July 2014 to version 4 dated 16 Nov. 2014](#)

[Summary of changes from version 4 dated 16 Nov. 2014 to version 6 dated 07 Oct. 2015](#)

[Summary of changes from version 5 dated 07 Oct. 2015 to version 7 dated 20 July 2017](#)

[Summary of changes from version 6 dated 07 Oct. 2015 to version 8 dated 29 Aug. 2017](#)

Dexcel Pharma Technologies Ltd

Protocol No.: CLI/016P

Protocol Title: The Efficacy and Safety of Chlorhexidine Gluconate Chip (PerioChip®) in Therapy of Peri-Implantitis

Clinicaltrial.gov Identifier: NCT02080403

EudraCT Number: 2013-00038-28

Summary of changes from version 1 dated 02 Nov. 2013 to version 2 dated 22 Jan. 2014		
Page/Section	Original Text (version 1)	Amended Text (version 2)
All through the protocol	Number of subjects that are expected to be randomized to the study 230 (115 at each study group)	Number of subjects that are expected to be randomized to the study 246 (123 at each study group)
All through the protocol	Number of subjects that are expected to be screened to the study 288	Number of subjects that are expected to be screened to the study 336
All through the protocol	Study expected power 80% and statistical significance level 4% for all statistical analysis and comparisons	Study expected power 85% and statistical significance level 5% for all statistical analysis and comparisons
Page 22 - Study Design and Duration	The duration of patient follow-up will be 25-28 weeks (including Screening), with interim visits at 0, 2, 4, 6, 8, 10, 12, 16 and 24 weeks	The duration of patient follow-up will be 25-28 weeks (including Screening and hygienic phase visits), with interim visits at 0, 2, 4, 6, 8, 10, 12, 16 and 24 weeks
Page 40 - Randomization Code	The randomization will be performed with stratification to study sites smoking habits and Baseline PD measurement in balanced blocks, each block containing 6 subjects. A total number of 48 blocks will be prepared for a total of 288. Each site will receive 4 types of lists by the defined stratification (smokers with PD 5 mm, smokers with PD 6-8 mm, non-smokers with PD 5 mm and non-smokers with PD 6-8 mm). This number already includes 10 blocks for spare.	The randomization will be performed with stratification to study sites smoking habits and Baseline PD measurement in balanced blocks, each block containing 6 subjects (3 per treatment Subgingival debridement + PerioChip® and 3 per treatment Subgingival debridement alone). A total number of 56 blocks will be prepared for a total of 336 subjects. Randomization blocks will be sent to the sites by the study data management Statistician . Each site will receive 4 types of lists by the defined stratification (smokers with PD 5 mm, smokers with PD 6-8 mm, non-smokers with PD 5 mm and non-smokers with PD 6-8 mm). Additional blocks will be provided to the sites according to the recruitment rate . This number already includes 10 blocks for spare.
Page 41 – Sample size	Statistical significance level was set to 4% since an Interim Analysis, that will use 1% of the total significance level, is planned.	Statistical significance level for all statistical analysis was set to 4% since an Interim Analysis that will use 1% of the total significance level, is planned 5.
Page 42 - Analysis population	Intent-to-treat (ITT) population – all patients randomized for one of the treatment arms and treated with at least one chip of study treatment or underwent Subgingival debridement will be used for all safety evaluations	Intent-to-treat (ITT) population – all patients randomized for one of the treatment arms and treated with at least one chip of study treatment or underwent Subgingival debridement will be used for assessments related to efficacy and all safety evaluations

Page 44 - Efficacy analysis and statistical models	Analysis for the number of pockets with at least 1 mm reduction in PD, and analysis for BOP for the target implant/s measured at each visit will be analysed by a Chi-square test or Fisher's exact test as is appropriate	Analysis for the number of pockets with at least 1 mm and at least 2 mm reduction in PD, and analysis for BOP for the target implant/s measured at each visit will be analysed by a Chi-square test or Fisher's exact test as is appropriate
Page 11- Protocol synopsis and Page 46 - Interim Analysis	An interim analysis is planned when 30 patients in each group have completed 24 weeks of therapy. Interim analysis will include primary efficacy endpoint and safety assessment. The purpose of the interim analysis is to achieve a primary assessment for the study safety and efficacy endpoints. The primary efficacy endpoint will be tested using a 0.01 significance level. 1% (0.01) of the overall type 1 error for this study of 5% will be used in the interim analysis. The final analyses will be tested with statistical significance level of 4% (0.04). The levels of significance will maintain an overall P value of 0.05 (Peto, Pike, Armitage, Breslow, Cox, Howard, et al. 1976	An interim analysis is planned when 30 patients in each group have completed 24 weeks of therapy. Interim analysis will include primary efficacy endpoint and safety assessment. The purpose of the interim analysis is to achieve a primary assessment for the study safety and efficacy endpoints. The primary efficacy endpoint will be tested using a 0.01 significance level. 1% (0.01) of the overall type 1 error for this study of 5% will be used in the interim analysis. The final analyses will be tested with statistical significance level of 4% (0.04). The levels of significance will maintain an overall P value of 0.05 (Peto, Pike, Armitage, Breslow, Cox, Howard, et al. 1976

Summary of changes from version 2 dated 22 Jan. 2014 to version 3 dated 13 July 2014

Page/Section	Original Text (version 2)	Amended Text (version 3)
Page 20 - Study Design and Duration		The reason for preferring the above design over the Double-blind, Placebo-controlled design is that in previous clinical studies with PerioChip® it was evident that when used Placebo chips have worse clinical outcome compare to No-chip. Namely, periodontal pockets treated with Placebo chips showed less improvement in PD and attachment levels compare to No-chip treated pockets. It was also noted that at six months following the use of Placebo chips fewer incidences of patients were considered to have healthy pockets. The results of these studies suggest, that placing of the Placebo chip acting as a mechanical barrier preventing environmental/outsides improvement in the pockets (Perio Products-I; Perio products-II). Due to the above mentioned findings the use of Placebo treatment arm is less adequate. In this case excluding the Placebo arm from the study design ultimately prevents the establishment of Double-blind procedure.
Page 39 - Statistical methods		It is worth noting that although parameters used in the above calculation are derived from a placebo-controlled design, it is reasonable to assume this calculation is more conservative than if the parameter used were taken from previous studies where the study design included a treatment arm with no chip assigned, in Periodontitis patients. In other words, the sample size calculation is based on sound data derived from a study design which used the same indication (periimplantitis) and treatment regimen (frequent chip insertion) as appear in the current protocol

Dexcel Pharma Technologies Ltd

Page 58 - Reference List		
23. Perio Products.I. Clinical effects following subgingival administration of Chlorhexidine gluconate (2.5 mg) in a cross-linked gelatin matrix (PerioChip) in patients with periodontal disease (study 91-011). Clinical Study Report
 
24. Perio Products. II. Clinical effects following subgingival administration of Chlorhexidine gluconate (2.5 mg) in a cross-linked gelatin matrix (PerioChip) in patients with periodontal disease (study 91-013). Clinical Study Report

--------------------------	--	---

Summary of changes from version 3 dated 13 July2014 to version 4 dated 16 Nov. 2014

Page/Section	Original Text (version 3)	Amended Text (version 4)
Page 7 - Protocol Synopsis; Page 22 - Inclusion Criteria	Inclusion Criteria 1 "Signed and dated informed consent"	Inclusion Criteria 1 "Signed and dated informed consent. The patient is of age and is capable of understanding the nature, significance and implications of the clinical trial and to form a rational intention in the light of the facts. "
Page 8 – Protocol synopsis; Page 24 - Exclusion Criteria	Exclusion Criteria 9: "Patients treated with systemic antibiotic therapy or periodontal/mechanical/local delivery therapy within 6 weeks prior to study entry and throughout the study duration."	Exclusion Criteria 9: "Patients treated with systemic antibiotic therapy or periodontal/mechanical/local delivery therapy within 6 weeks prior to study entry and throughout the study duration. In case the investigator advises the patient that antibiotic therapy is required during the course of the study, the patient should be excluded from further participation. "
Page 25 - Patient Discontinuation/ Withdrawal Criteria	"Patient receives emergency dental treatment which may interfere with the assessment of study endpoints."	"Patient receives emergency dental treatment including target implant explanation which may interfere with the assessment of study endpoints. Paragraph was added: "Despite participating in the study, patient, who in the opinion of the investigator displays an inadequate response to subgingival debridement and chemical disinfection during the study period, may be entitled to surgical therapy of peri-implantitis." "
Page 26 - Concomitant Medication Treatment	Patients will be instructed to refrain from: "Any use of Chlorhexidine oral rinses/mouthwashes during the study"	Patients will be instructed to refrain from: "Any use of Chlorhexidine oral rinses/mouthwashes during the study without consulting the Investigator in advance. "

Summary of changes from version 3 dated 13 July2014 to version 5 dated 07 Oct. 2015

Page/Section	Original Text (version 3)	Amended Text (version 5)
Page 7 - Protocol Synopsis	Number of clinical sites "5 clinical sites" to "at least 5 clinical sites"	Number of clinical sites "at least 7 clinical sites"
Page 13; Page 28; Page 37 - Study Schedule	Last visit number "visit 9" The allowance (window)of final visit "90 ±10 days from previous visit"	Last visit number "visit 10" The allowance (window)of final visit " 56±10 days from previous visit (8 weeks) "

Dexcel Pharma Technologies Ltd

Summary of changes from version 4 dated 16 Nov. 2014 to version 6 dated 07 Oct. 2015		
Page/Section	Original Text (version 4)	Amended Text (version 6)
Page 7 - Protocol Synopsis	Number of clinical sites "5 clinical sites" to "at least 5 clinical sites"	Number of clinical sites "at least 7 clinical sites"
Page 13;Page 29; Page 38 -Study Schedule	Last visit number "visit 9" The allowance (window)of final visit "90 ±10 days from previous visit"	Last visit number "visit 10 " The allowance (window)of final visit " 56±10 days from previous visit (8 weeks) "
Summary of changes from version 5 dated 07 Oct. 2015 to version 7 dated 20 July 2017		
Lines	Original Text (version 5)	Amended Text (version 7)
Headline (First Page)		
8 - 9	Date : 07 October 2015	Date : 02 August 2017
8 - 9	Version : 5	Version : 7
19	Footer date: 07 October 2015 Footer version: Protocol # CLI/016P – version 5	Footer date: 02 August 2017 Footer version: Protocol # CLI/016P – version 7
Table of Contents		
39-41	5.3 page 24;	5.3 page 25 ;
42 - 44	5.4 page 25;	5.4 page 26 ;
45 - 80	6. Page 26; 6.1 page 28; 6.2 page 29; 6.2.1 page 29; 6.2.2 page 32; 6.2.3 page 34; 6.2.4 page 36; 6.2.5 page 36; 6.2.5 page 36; 6.3 page 37; 6.3.1 page 37; 6.3.2 page 37; 6.3.3 page 37;	6. Page 27 ; 6.1 page 29 ; 6.2 page 30 ; 6.2.1 page 31 ; 6.2.2 page 33 ; 6.2.3 page 35 ; 6.2.4 page 37 ; 6.2.5 page 37 ; 6.2.5 page 37 ; 6.3 page 38 ; 6.3.1 page 38 ; 6.3.2 page 38 ; 6.3.3 page 38 ;
81-95	7. Page 37; 7.1 page 37; 7.2 page 37; 7.3 page 38; 7.4 page 39;	7. Page 38 ; 7.1 page 38 ; 7.2 page 39 ; 7.3 page 40 ; 7.4 page 40 ;
96-125	8. Page 39; 8.1 page 39; 8.2 page 40; 8.3 page 40; 8.3.1 page 40; 8.3.2 page 40; 8.3.3 page 41; 8.4 page 41; 8.5 page 44; 8.6 page 44;	8. Page 46 ; 8.1 page 40 ; 8.2 page 41 ; 8.3 page 42 ; 8.3.1 page 42 ; 8.3.2 page 42 ; 8.3.3 page 42 ; 8.4 page 42 ; 8.5 page 45 ; 8.6 page 46 ;
126-140	9. page 45; 9.1 page 45; 9.2 page 46; 9.3 page 46; 9.4page 47;	9. page 46 ; 9.1 page 46 ; 9.2 page 47 ; 9.3 page 48 ; 9.4 page 48 ;
141-146	10. page 48; 10.1 page 48;	10. page 49 ; 10.1 page 49 ;
Clinical Study Protocol - Overview		
203	Date : 07 October 2015	Date : 02 August 2017
Protocol Synopsis - Number of patients		
221-224	A total of 246 patients in at least five clinical sites will be randomized. 123 patients for the Subgingival debridement + PerioChip® arm, and 123 patients for Subgingival debridement alone arm	A total of 290 patients in at least nine clinical sites will be randomized. At least 123 patients for the Subgingival debridement + PerioChip® arm, and at least 123 patients for Subgingival debridement alone arm will complete all required study visits, considering withdrawal rate estimation of between 12%-15%
Protocol Synopsis - Inclusion Criteria #5		

Dexcel Pharma Technologies Ltd

248-254	The patient has at least one implant in the oral cavity with clinical and radiographical signs of peri-implantitis. In the affected implant, at least one of the four aspect measured (mesio-buccal, mid-buccal, disto-buccal and mid-lingual) must show radiographic evidence of bone loss of at least 3 mm from implant shoulder, and at least 2 mm distal and mesial supporting bone left from the apex to the coronal direction, in combination with bleeding and/or suppuration on probing and a peri-implant Probing Depth (PD) of 5-8 mm.	The patient has at least one implant in the oral cavity with clinical and radiographical signs of peri-implantitis. In the affected implant, at least one of the four aspects measured [mesio-buccal (MB), mid-buccal (MiB), disto-buccal (DB) and mid-lingual (MiL)] must show radiographic evidence of bone loss of at least 3 mm from implant shoulder, and at least 2 mm distal and mesial supporting bone left from the apex to the coronal direction, in combination with bleeding and/or suppuration on probing and a peri-implant Probing Depth (PD) of 5-8 mm.
Protocol Synopsis - Exclusion Criteria #10		
273-276	Patients chronically (i.e. two weeks or more) treated with non-steroidal anti-inflammatory drugs (NSAIDs) or any medications known to affect soft tissue condition (excluding treatment of Acetylsalicylic acid \leq 100 mg/day).	Patients chronically (i.e. two weeks or more) treated with non-steroidal anti-inflammatory drugs (NSAIDs), or any medications known to affect soft tissue condition (excluding treatment of Acetylsalicylic acid \leq 100 mg/day). A comprehensive list can be found in the Patient information sheet – list of prohibited medications.
Protocol Synopsis - Exclusion Criteria #11 (New)		
277-283		11. Patients with any history of use of Medications known to cause Medication related osteonecrosis of the jaw: Bisphosphonates, RANKL inhibitors, Antiangiogenic agents and m-TOR inhibitors administered Intravenously (IV), Intramuscularly (IM) or Subcutaneously (SC). Patients with a history of a one year or more of Per-Os (PO) use of the medications known to cause Medication related osteonecrosis of the jaw , with last dose being under 3 months prior to the screening visit, and a CTX test value of $<$ 150 ng/ml.
Protocol Synopsis - Exclusion Criteria 12 - 16		
284-285	11. Patients with uncontrolled diabetes, of any type, and/or patients with HbA1c test value $>$ 7.5% dated 3 months prior to the screening visit.	12. Patients with uncontrolled diabetes, of any type, and/or patients with HbA1c test value $>$ 7.5% dated 3 months prior to the screening visit.
286-287	12. Patients receiving radiation therapy to the head and neck area and/or receiving immunosuppressive therapy.	13. Patients receiving radiation therapy to the head and neck area and/or receiving immunosuppressive therapy.
288-289	13. The presence of any medical or psychiatric condition or any other condition that, in the opinion of the Investigator, could affect the successful participation of the patient in the study.	14. The presence of any medical or psychiatric condition or any other condition that, in the opinion of the Investigator, could affect the successful participation of the patient in the study.
290	14. Drug and alcohol abuse.	15. Drug and alcohol abuse.
291-292	15. Patient participates in any other clinical study 30 days prior to the start of the study and throughout the study duration.	16. Patient participates in any other clinical study 30 days prior to the start of the study and throughout the study duration.
Protocol Synopsis – Statistical Methods – Sample Size		
315-321	A total of 246 patients will be randomized, 123 patients for the	A total of up to 290 patients will be randomized. At least 123 patients

	
Subgingival Debridement + PerioChip® arm and 123 patients for the Subgingival Debridement alone arm.
 
Based on previous phase IIa studies, the expected drop-out rate in this study will be between 20%-25%. Thus, it is estimated that approximately 336 patients will be screened in order to randomize 246 patients.
	
for the Subgingival Debridement + PerioChip® arm and 123 patients for the Subgingival Debridement alone arm to complete all required study visits.
 
Based on the current drop-out rate (after randomization) of 9%, the expected drop-out rate (after randomization) should be between 12%-15%
 
Based on previous phase IIa studies, the expected drop-out rate in this study will be between 20%-25%. Thus, it is estimated that approximately 375 patients will be screened in order to randomize up to 290 patients that complete all required study visits.

Abbreviations		
401-402	4 abbreviations regarding pocket aspects were not listed	MB - Mesio-Buccal; MiB - Mid-Buccal; DB - Disto-Buccal; MiL-Mid-Lingual
Study Schedule		
404-413	
Evaluations/Activity Column: "dental Radiography
 
SuperScript #1: Dental Radiography evaluation dated within 1 (one) year prior the Screening visit
 
SuperScript #2: In case chips are pop-out recurrently in visits 3, 5 and 7 a pocket examination will be conducted by the designated examiner to verify $PD \geq 5$ mm
 
SuperScript #6: Chip/s will be inserted only in target implant/s which had previously received a chip and which pocket depth at those visits is ≥ 5 mm and which pocket depth at those visits is ≥ 5 mm" was removed
	
Evaluations/Activity Column: "Periapical dental Radiography
 
SuperScript #1: "Periapical" Dental Radiography evaluation dated within 1 (one) year prior the Screening visit.
 
SuperScript #2: In case chips are pop-out recurrently in visits 3, 4, 5 and 7 a pocket examination will be conducted by the designated examiner to verify $PD \geq 5$ mm
 
SuperScript #6: Chip/s will be inserted only in target implant/s which had previously received a chip and which pocket depth at those visits is ≥ 5 mm

Study Design and Duration		
621	The same examiner will perform all the measurements during the study.	Calibrated examiners will perform all the measurements during the study.

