7.2 Randomization Codes		
1044-1045	A total number of 56 blocks will be prepared for a total of 336 subjects.	Line removed
1050	This number already includes 10 blocks for spare	Line removed

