1.2 Design

This study is a multi-center, randomized, single-blind masking, parallel, two-arm clinical study.

The study duration will be 25-28 weeks (6 months) and will comprise a total of 10 visits: Screening and hygienic phase therapy (weeks -3 to -1), Baseline (week 0), week 2, week 4, week 6, week 8, week 10, week 12, week 16 and week 24 (follow up visit).

During the Baseline visit, eligible patients will be randomized to one of the following treatment regimens:

Treatment 1 – Subgingival debridement + Chlorhexidine Gluconate chip (PerioChip®) inserted every fortnight, for the first 12 weeks.

Treatment 2 – Subgingival debridement.

These treatments will be applied for at least 1 (one) and not more than 2 (two) implants in the oral cavity with clinical and radiographical signs of peri-implantitis. Peri-implantitis is defined as marginal bone loss of at least 3 mm from implant shoulder, and at least 2 mm distal and mesial supporting bone left from the apex to the coronal direction, in combination with bleeding and/or suppuration on probing and a peri-implant Probing Depth (PD) of 5-8 mm.

All pocket measurements (PD, BOP and R) and chip insertions will be made in the same order of procedures every time.

The same examiner will perform all the measurements during the study.

The person (physician/hygienist) placing the Chlorhexidine chips in the periodontal pockets or performing the Subgingival debridement, according to the randomization, will not be involved in target pockets measurements (i.e. the examiner and the physician/hygienist placing the chip or performing the Subgingival debridement will be two different persons).

In each patient meeting the entrance criteria, the deepest periodontal pocket of at least 1 (one) and no more than 2 (two) implant/s (if available) will be selected as a target pocket, and will be used for chip/s insertion or Subgingival Debridement and as the primary efficacy end-point.

The target pocket in the selected implant/s, will be treated at each visit with the same treatment arm, initiated at Baseline visit, as described below.

Implant/s which were not selected as target implant/s will be treated as per the investigators discretion as long as it does not affect the study inclusion/exclusion criteria (e.g. treatment with antibiotics or surgery next to a target implant included in the study).

Treatment 1: (PerioChip®)

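### A stated, fixed block size of 6, with blocks sent to sites and an unmasked operator, could let someone who tracks a site's list foresee about 18-19% of allocations

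*Protocol*

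**What the plan says.** The supplied protocol document is a set of change logs. The entry on the randomization code in the version 1 to version 2 log gives the scheme:

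- Allocation uses "stratification to study sites smoking habits and Baseline PD measurement", "in balanced blocks, each block containing 6 subjects (3 per treatment" arm).
- "Each site will receive 4 types of lists by the defined stratification": smokers or non-smokers, crossed with a baseline pocket depth of 5 mm or 6-8 mm.
- "Randomization blocks will be sent to the sites by the study data management Statistician", with more blocks supplied as recruitment requires.

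The version 7 and version 8 logs for section 7.2 delete only two lines. One is the total ("A total number of 56 blocks will be prepared for a total of 336 subjects") and the other is the remark on spare blocks. No log entry changes the block size or where the blocks go.

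On masking, SAP 1.2 states: "This study is a multi-center, randomized, single-blind masking, parallel, two-arm clinical study". The version 3 log explains that "excluding the Placebo arm from the study design ultimately prevents the establishment of Double-blind procedure". SAP 1.2 separates the examiner from the operator: the person who places the chip or does the debridement, "according to the randomization, will not be involved in target pockets measurements".

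**The concern.** A balanced block must end level, so its last allocations follow from the earlier ones. Someone who knows the block size, where the block began and what has been given so far can work them out. Three features of this plan make that easier: the size is constant and written in the protocol, each list belongs to a single site, and the operator learns the arm of every patient they treat.

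The risk is selection before allocation. A site that foresees the next arm can enrol, defer or decline a borderline patient accordingly. The separate examiner protects the measurements made after allocation, but does not act on who is entered. The adjustment in SAP 3.3.1 (age, gender, smoking, site, baseline measurement) cannot remove selection on factors that were not recorded. SAP 3.2.1 keeps the baseline comparison descriptive.

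**Working it through.** **The plan's own figures.** The documents give no figure for predictability. The deleted totals agree with the stated block size: 56 × 6 = 336. The sample size in SAP 1.8 (difference 0.50 mm, SD 1.30, two-sided 5%, 85% power) reproduces: 2 × (1.960 + 1.036)² × 1.30² / 0.50² = 121.4, or 122 per arm. Power at 123 per arm by the noncentral t distribution is 85.2%. With 15% drop-out, 246 / 0.85 = 289.4, or 290. Block size does not enter any of these.

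**One complete block.** A 3:3 block has 20 possible orders, all equally likely. An allocation is certain once one arm has used its three places. A best guess always names the arm with more places left.

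| Position | 1 | 2 | 3 | 4 | 5 | 6 | Sum |
|---|---|---|---|---|---|---|---|
| Certain | 0 | 0 | 0 | 2/20 = 0.1 | 8/20 = 0.4 | 1 | 1.5 |
| Best guess right | 0.5 | 0.6 | 0.6 | 0.7 | 0.7 | 1 | 4.1 |

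The certain share is 1.5/6 = 25%. The best guess succeeds 4.1/6 = 68.3% of the time, against 50% if nothing can be predicted.

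**The trial at its planned size.** Inputs: 290 patients and at least nine sites (version 8 log, number of patients), with four lists per site. That is 9 × 4 = 36 lists and 290/36 = about 8 patients per list.

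A list of 8 is one full block plus two patients whose allocations are never certain:

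- Certain: 1.5/8 = 18.75%.
- Best guess: (4.1 + 0.5 + 0.6)/8 = 5.2/8 = 65%.

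Letting list sizes vary at random, by simulation with sites of equal expected size:

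| Sites | Four strata equal | Strata split 5/15/20/60% |
|---|---|---|
| 5 | 21.4% | 21.3% |
| 7 | 19.9% | 20.1% |
| 9 | 18.6% | 18.8% |
| 12 | 16.3% | 16.9% |

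Equal site sizes and the stratum splits are assumptions; the documents give neither.

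**Varying block sizes.** The observer here knows the set of sizes and all past allocations in the list, but not where blocks begin. Share of certain allocations, by simulation:

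| List length | Fixed 6 | 4 and 6 | 4, 6 and 8 |
|---|---|---|---|
| 8 | 18.9% | 6.0% | 2.9% |
| 12 | 25.0% | 6.4% | 2.5% |
| 24 | 25.0% | 5.8% | 2.5% |

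The gain depends on hidden boundaries. If an observer could see where each block starts and how long it is, the expected number of certain allocations would be 1.33, 1.5 and 1.6 per block of 4, 6 and 8. The share for complete blocks would then be (1.33 + 1.5 + 1.6)/18 = 24.6%, almost the same as now.

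**The case against.** The best counter-argument is that prediction needs more than the documents establish. Whoever enrols must know the block size, the block boundaries and every earlier allocation in that site's stratum list. SAP 1.2 shows only that the operator acts on the allocation and does not measure the target pockets. It does not say that the operator enrols patients or follows the four lists, and a site may have several operators. This stands, and it is why the figures are ceilings.

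A reader might also infer that the lists lie open at the sites. The documents do not support that. Sending blocks to sites is compatible with sealed assignments as well as with open lists, and the full text of sections 7.2 and 7.3 is not supplied. Concealment is undescribed here, not shown to be absent. Nor do the documents show that the block size was public during recruitment: it stood in the protocol, and the released summary is dated April 2021.

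The room for steering is also limited. Eligibility rests on measured thresholds, SAP 1.2 makes the deepest pocket of a chosen implant the target, and the primary model adjusts for baseline depth. These points reduce the scope. They leave open whether and when a patient is entered, and they do not cover unrecorded prognosis.

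**Conclusion.** The point holds as a weakness of the allocation scheme. A tracker of one list could foresee up to 25% of allocations if every block fills. At 290 patients over nine sites the figure is about 18-19%, with a best guess right about 65% of the time; for 12 down to 5 sites the certain share is 16-21%. These figures assume equal site sizes and an observer with full knowledge of the list.

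It would be tempting to say that a quarter of this trial's allocations are predictable. That is the complete-block value, and about eight patients per list leaves many last blocks unfilled. It would also go too far to say that selection took place, since nothing in the documents shows who could use the information. The remedy is a cheap improvement, not a correction of an error, and the stated sample size and power are untouched.

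**What to change.** In section 7.2, replace the fixed block of 6 with block sizes that vary at random (for example 4 and 6, or 4, 6 and 8) within the same strata. State in the protocol only that permuted blocks of varying size are used, and put the sizes in a restricted randomisation document. Because further blocks are supplied as recruitment proceeds, supply them in a form that does not show where a block ends; otherwise the gain is lost.

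If sections 7.2 and 7.3 do not already do so, they should also say how assignments are concealed at the site and who enrols. For lists already used, that description belongs in the study report.

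The cost is a set of new lists, a wording change and slightly more imbalance between arms in small strata.
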